## **E.5. Inclusion of Women, Minorities, and Children**

### **E.5.1. Inclusion of Women and Minorities**

Given that two of the cancer types included in the study are exclusive of women, we expect that the percentage of women (60%) in the sample will be higher than men. The inclusion of minorities in the proposed study is driven by the characteristics of the patient population undergoing cancer treatment at the Moffitt Cancer Center. The "Targeted/Planned Enrollment Table" displays the expected level of participation by minorities. The Moffitt Cancer Center makes ongoing, active efforts to increase patient diversity. Dr. [name], as the Executive Director of Institutional Diversity, has increased advertisements and announcements for the Moffitt Cancer Center distributed at community events and churches that are preferentially frequented by minorities. Hispanic and African American advisory boards were created, patient navigation programs were developed, and outreach efforts to local minority physicians and religious leaders were increased. All these efforts resulted in the classification of Moffitt Cancer Center at the number 4 ranked health care facility on Diversity Inc's 2017 "Top Hospitals & Health Systems" list. Based on these initiatives and on our planned efforts to compose a diverse sample, we expect that approximately 10% of the sample will include Hispanic/Latino patients, and approximately 15% will be African American.

### **E.5.2. Inclusion of Children**

The diseases under investigation occur most frequently in adults, with median age at diagnosis of 73 for bladder cancer, 62 for breast cancer, 67 for colorectal cancer, between 49 and 63 for gynecological cancers, and 64 for skin melanoma. Moreover, Moffitt Cancer Center does not treat pediatric patients. Therefore, we do not anticipate any children will be enrolled in these studies.

## **E.6. Recruitment and Retention Plan**

Similar to our prior studies, we will use an existing electronic system that will allow sorting for patients reporting current smoking. In coordination with clinical staff, potential participants will be called over the phone or approached during medical visits and informed about the aims of the study. If interested, they will be screened and those meeting inclusion criteria will be invited to participate. To maximize our recruitment rates, the interview will take place on the same day of a medical visit, if possible. Thus, after obtaining informed

consent, the research assistant will escort the participant to a room where the interview will be conducted. However, if necessary, the interview will be scheduled for another day or conducted over the phone. Participants will be compensated \$20 in cash if the study is conducted in person or in the form of a gift card or electronic gift card for the same value if conducted remotely.

Since there are no follow-ups in Study I, a Retention Plan is not provided.

## **E.7. Study Timeline**

Preparation of baseline measures and interview materials	Month 1
Study I recruitment and in-depth interviews	Months 2-5
Development of intervention materials and elaboration of first draft of intervention	Months 6-7
Learner Verification, modification and final draft of intervention	Months 8-11
Manuscript preparation: development of intervention materials	Months 12-13

## **F. PROTECTION OF HUMAN SUBJECTS STUDY II**

### **F.1. Risks to Human Subjects**

#### **F.1.1. Human subjects Involvement, Characteristics, and Design**

In this study, we will evaluate if the intervention is feasible (e.g., screening, recruitment, completion of assessment measures, and follow-up) and acceptable (e.g., self-reported patient satisfaction and number of participants reading the study materials).

Participants in this study will be 50 individuals who recently (i.e., within 6 months) received a diagnosis of breast, colorectal, gynecological, skin melanoma, and bladder cancer at Moffitt Cancer Center. To be eligible for the study, participants must: a) have smoked at least 1 cigarette in the previous month; b) be able to read and write English; c) not currently enrolled in a smoking cessation program; and d) be able to give informed consent. Patients with distant metastases will be excluded, as participation may be burdensome. Male patients diagnosed with breast cancer will be excluded as lifetime risk for breast cancer in men is very low (less than 1% of breast cancer worldwide).

#### **F.1.2. Study Procedures, Materials, and Potential Risks**

This study does not involve any deception. Potential participants will be approached or called over the phone by a trained research assistant and will be screened for eligibility criteria using a brief eligibility screening form. Eligible patients will be asked if they would like to participate in a study of tobacco use by cancer patients. They will be asked to review a consent form and will be provided the opportunity to ask any questions. Informed consent and consenting procedures will adhere to the Advarra Institutional Review Board guidelines. Patients will be consented verbally and will be provided a copy of the informed consent for their records (via email or mail for those patients who consent over the phone). We will request a waiver of documentation of consent from the IRB.

Following the informed consent, participants will complete a baseline questionnaire and will be given the intervention materials. They will be contacted a week and a month later for a follow-up assessment. The following materials will be used:

- c. Questionnaires measuring sociodemographic characteristics, smoking history and nicotine dependence, perception of smoking relatedness of their cancer, risk perception, affective and emotional response, self-image, motivation, and treatment satisfaction.
- d. Breath to be analyzed for carbon monoxide from subjects who self-report smoking abstinence at follow-ups.

Participants may be sharing personal information about themselves in the questionnaires. In addition, tobacco smoking for cancer patients may be a sensitive topic due to perceived stigma. Thus, in the event that a patient appears distressed, a social worker will be available to assist with making the appropriate referrals.

## **F.2. Adequacy of Protection Against Risks**

### **F.2.1. Informed Consent and Assent**

Potential participants will be approached by a trained research assistant during a visit to the Moffitt Cancer Center or called over the phone. They will be screened for eligibility criteria using a brief eligibility screening form. Eligible patients will be asked if they would like to participate in a study of tobacco use by cancer patients. For in-person visits, patients willing to participate will be escorted to a private room where the research assistant will explain the informed consent. Then, they will be asked to review the consent form and will be provided the opportunity to ask any questions. Patients who are contacted over the phone will receive a verbal explanation of the informed consent, they will have the opportunity to ask questions, and will be sent a copy via mail or email for their records. Informed consent and consenting procedures will adhere to the Advarra Institutional Review Board guidelines. We will request a waiver of documentation of consent from the IRB. Patients not able to provide informed consent will be excluded from the Study.

### **F.2.2. Protections Against Risk**

The potential risks are judged to be minor. We recognize that some patients may experience some discomfort in completing the measures. In the event that a patient appears distressed, a social worker will be available to assist with making the appropriate referrals.

Patients may provide personal information about themselves during the screening or questionnaires. All research staff will receive training in research ethics. Confidentiality will be maintained by using subject numbers on data, rather than subjects' names. Subject data will be available only to research staff. Paper data will be kept in locked filing cabinets in locked laboratory rooms; electronic data will be stored on password-protected, secured servers at Moffitt Cancer Center. Identifying information will not be reported.

## **F.3. Potential Benefits of the Proposed Research to Research Participants and Others**

The potential risks are judged to be minor. We recognize that some patients may experience some discomfort in completing the measures. In the event that a patient appears distressed, a social worker will be available to assist with making the appropriate referrals. The main benefit to participants is involvement in research that may lead to the development of interventions to help cancer patients to increase their motivation to quit smoking. However, participation may motivate some patients to quit smoking, which has multiple health benefits, particularly for this population.

## **F.4. Importance of the Knowledge to be Gained**

Improved knowledge regarding how to increase smoking cessation motivation in patients with a cancer not widely known to be related to smoking could have dramatic public health implications. The ultimate aim of this study is to motivate patients to eventually quit smoking, which will improve health, quality of life, and survival for these individuals.

## **F.5. Inclusion of Women, Minorities, and Children**

### **F.5.1. Inclusion of Women and Minorities**

Given that two of the cancer types included in the study are exclusive of women, we expect that the percentage of women (60%) in the sample will be higher than men. The inclusion of minorities in the proposed study is driven by the characteristics of the patient population undergoing cancer treatment at the Moffitt Cancer Center. The "Targeted/Planned Enrollment Table" displays the expected level of participation by minorities. The Moffitt Cancer Center makes ongoing, active efforts to increase patient diversity. Dr. [name], as the Executive Director of Institutional Diversity, has increased advertisements and announcements

for the Moffitt Cancer Center distributed at community events and churches that are preferentially frequented by minorities. Hispanic and African American advisory boards were created, patient navigation programs were developed, and outreach efforts to local minority physicians and religious leaders were increased. All these efforts resulted in the classification of Moffitt Cancer Center as the number 4 ranked health care facility on Diversity Inc's 2017 "Top Hospitals & Health Systems" list. Based on these initiatives, and on our planned efforts to compose a diverse sample, we expect that approximately 10% of the sample will include Hispanic/Latino patients, and approximately 15% will be African American.

#### **F.5.2. Inclusion of Children**

The diseases under investigation occur most frequently in adults, with median age at diagnosis of 73 for bladder cancer, 62 for breast cancer, 67 for colorectal cancer, between 49 and 63 for gynecological cancers, and 64 for skin melanoma. Moreover, Moffitt Cancer Center does not treat pediatric patients. Therefore, we do not anticipate any children will be enrolled in these studies.

#### **F.5.3. Recruitment and Retention Plan**

We will use an existing electronic capture that will allow sorting for patients reporting current smoking. Potential participants will be called over the phone or approached during medical visits and informed about the aims of the study. If interested, they will be screened and those meeting inclusion criteria will be invited to participate. The research assistant will escort the participant to a room where they will go through the informed consent. After consenting, patients will receive the intervention materials. However, if necessary, this session will be scheduled for another day or conducted remotely to accommodate to patients' preferences. Patients recruited over the phone will receive the study materials over the mail and/or email. All participants will be contacted again one week and one month after receiving the intervention materials. To increase retention rates, follow-up assessments will be conducted during a scheduled medical visit, but we will offer phone, electronic, and mail options to accommodate patients' individual situations and preferences. To increase retention of participants in the study, they will be compensated \$15 for completing the pre- and post-intervention and \$20 for completing the 1-month follow-up in cash if the study is conducted in person, or with a gift card or electronic gift card for the same value if it is completed online or over the phone.

#### **F.5.4. Study Timeline**

Intervention delivery, assessment of acceptability and feasibility	Months 12-21
Follow-up assessments	Months 13-22
Manuscript preparation: feasibility and acceptability outcomes	Months 22-24

### **F.6. Data and Safety Monitoring Plan**

#### **F.6.1. Overview**

Although this is an extremely minimal risk study, the Principal Investigator, [name], will implement a DSMP to ensure that the expected risk/benefit ratio is maintained throughout the study and that the confidentiality and accuracy of the data are preserved. The research assistant will receive formal training in the Division of Population Sciences about ethical conduct of research, consenting participants, implementation of study protocols, etc. In addition, he/she will be trained by the PI on recruitment, interviewing, and data collection. All members of the study team will receive training in research ethics and HIPAA procedures, as well as study-specific training provided during research team meetings. The study team will meet weekly to discuss study progress, including participant recruitment and retention, data management, any participant complaints, and confidentiality issues. Given the nature of the study, the probability of an adverse event occurring is extremely low. However, as per IRB policy, any serious or unexpected adverse events will be reported promptly (within 2-5 business days, depending on the nature of the event) to the IRB and the PRMC.

#### **F.6.2. Quality Assurance for Data Collection**

The PI and research assistant will meet weekly to discuss recruitment and data collection issues and the study team will meet biweekly to discuss any possible additional issues.

#### **F.6.3. Quality Assurance for Data Management**

Data will be collected via paper and pencil measures. Data entered by staff will be double-entered and compared for inconsistencies. Validity checks of data values and ranges will be conducted upon data entry and again prior to analysis. To ensure participant confidentiality, baseline and follow-up assessment data will not include any unique identifiers.

#### **F.6.4. Data Integrity and Security**

To protect confidentiality all participants in the study will be provided a study number not linked to their own patient or tumor IDs to avoid data breach. Once all data have been linked to individuals, all identifiers will be deleted. IRB approvals and participant documents will be kept in a locked location. All computers will be password-protected. Only trained grant personnel will have access to data.

#### **F.6.5. Identification of Adverse Effects**

Potential risks of the study are judged to be minor. In the case of a patient experiencing discomfort completing the measures or appearing distressed, a social worker will assist with making the appropriate referrals. The PI will monitor the study for adverse events and report adverse events to the institution's protocol monitoring committee, IRB, and funding sponsor as required.

### **F.8. Statistical Design and Power**

We expect to include a total of 50 cancer patients (10 per cancer site) in this study. Assuming follow-up of 80% of enrolled participants across the 5 cancer sites, 2-tailed  $\alpha$  of .05, and power ( $1-\beta$ ) of .80, this study will be powered to detect a small-medium effect size ( $f$ ) of .20.

Acceptability and feasibility will be evaluated using descriptive statistics. For acceptability we will assess patients' treatment satisfaction through the mean scores of a questionnaire based on the CSQ and open-ended feedback from participants. This questionnaire will also inform about how many participants read the intervention materials, which will be used as an indicator of demand (criterion:  $\geq 80\%$  of participants enrolled in Study II). Feasibility will be measured by the number of patients meeting inclusion criteria to participate in the study, agreement to participate in the study ( $\geq 75\%$  of those meeting inclusion criteria and approached to participate), percentage of participants completing baseline assessment measures ( $\geq 85\%$  of those who agree to participate in the study), and percentage of participants completing the one week and one-month follow-up assessment ( $\geq 80\%$  of those who completed baseline). Changes in cessation motivation and Teachable Moment Model variables will be assessed using repeated-measures Analysis of Variance (ANOVA). Finally, we will receive data from MCC's TTSSs on whether participants followed through with referrals to them and we will capture basic website analytics. These will serve as behavioral indicators of cessation motivation.

Other collected variables will also be examined on an exploratory basis. For example, sex differences will be analyzed, as will differences between cancers typically affecting women (gynecological, breast) versus men (bladder).

The pilot study will not include a control group, nor be powered to test moderator or mediator variables. However, results will inform on the feasibility and scope of a potential, subsequent RCT.

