**Specific Aim 2. To assess feasibility and acceptability of the intervention among the target populations.** Once the minimal intervention is developed in Aim 1, it will be distributed to cancer patients who are current smokers and have been diagnosed with one of the five cancer types above (N=50). We will evaluate if the intervention is feasible (e.g., screening, recruitment, completion of assessment measures, and follow-up) and acceptable (e.g., self-reported patient satisfaction). These data will provide valuable information in preparation for a subsequent, fully-powered randomized trial in which our motivational intervention will precede an evidence-based smoking cessation intervention.

In summary, the goal of the intervention is to harness the motivational power of this potential teachable moment beyond lung and H&N cancers. Given the clinical importance of smoking cessation to all cancer patients, this research has potential for wide impact upon cancer treatment outcomes and quality of life.

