**D.2.2. Study II (Specific Aim 2). Assessment of feasibility and acceptability (months 12-21).** We will evaluate patients' satisfaction (acceptability), and if the intervention is feasible and adequate for a future efficacy trial (e.g., screening, recruitment, completion of assessment measures, and follow-up). After completing a baseline questionnaire, 10 participants from each cancer type ( $n=50$ ) will receive a booklet/pamphlet corresponding to their specific cancer type. They will also be given an insert describing the smoking cessation services offered at MCC, with contact information for the tobacco treatment specialist (TTS) (*a professional trained to help tobacco users*). The insert will also include a link (both as a text-based address and as a QR code, to facilitate use) to a website where participants will find information for the Quitline and existing smoking cessation websites (e.g., smokefree.gov, tobaccofreeflorida.com, cancer.org/healthy/stay-

away-from-tobacco/guide-quitting-smoking). Each insert will have a personal code that will allow us to track who visited the study site. One week and one month later, participants will be contacted and assessed on whether they read the booklet/pamphlet (demand), change in the TMM elements (risk perception, emotional response, and self-image), and their motivation to quit smoking (preliminary efficacy). We will also assess their satisfaction with the intervention (acceptability). Finally, we will ask them if they contacted the TTS or if they would like us to make a referral for them, and we will count the number of participants who visited the study website. Although this study is not designed or powered to examine smoking cessation outcomes, we will assess smoking behavior and quit attempts to pilot the methods that would be used in a subsequent RCT. When institutional COVID policy allows, we will collect breath carbon monoxide (CO), using 5ppm as the cutoff [51, 52], to confirm self-reported abstinence from smoking. In cases for which follow-up is not conducted in-person, a session will be scheduled to conduct CO testing.

**D.2.2.1. Inclusion criteria.** Study II inclusion criteria will mirror those in section D.2.1.1.

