**D.2.2.2. Recruitment procedures and compensation.** Potential participants will be identified as described in section D.2.1.2, and will be compensated \$15 for completing pre- and post-assessment and \$20 for the one month follow-up in cash if the study is conducted in person, or with a gift card or electronic gift card for the same value if it is completed online or over the phone.

**D.2.3. Assessment and measures.** Participants will complete assessments at baseline, one week after the motivational intervention, and at 1-month follow-up (see Table 2). Post-intervention assessments will be conducted in person coordinated with a scheduled medical visit when possible, but we will offer phone, electronic, and mail options to accommodate patients' individual situations and preferences.

**Demographic and cancer-related variables.** Age, sex, education, marital status, and race/ethnicity will be included. Time since diagnosis, cancer stage and cancer treatment will be recorded from medical chart review.

**Tobacco measures.** Participants will complete the Cancer Patient Tobacco Use Questionnaire (C-TUQ) [49, 53], a 22-item questionnaire that assesses tobacco use among cancer patients in a rigorous and standardized way (e.g., number of years smoking, number of cigarettes per day, smoking behavior since cancer diagnosis). They will also complete the Fagerström Test for Nicotine Dependence (FTND) [54], a standard and validated measure of nicotine dependence [54, 55].

**Perception of smoking relatedness.** In absence of a validated measure, we will assess patients' perception of the role of smoking in the etiology and successful treatment of their cancer type using Likert scales and the Revised Illness Perception Questionnaire (IPQ-R) [65].

**TM measures.** For **perceived risk**, we will use the Perception of Risk (POR) [56] questionnaire that assesses how continued smoking affects cancer (e.g., "smoking after a diagnosis of cancer impairs physical healing").

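### Change over three assessments is analysed by repeated-measures ANOVA with no rule for incomplete cases; a mixed model on all available assessments is a cheap, modest improvement, though not a cure for every kind of dropout

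*Combined protocol and SAP*

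**What the plan says.** Section F.8 gives the whole analysis of change in one sentence: "Changes in cessation motivation and Teachable Moment Model variables will be assessed using repeated-measures Analysis of Variance (ANOVA"). The schedule in D.2.3 is "Participants will complete assessments at baseline, one week after the motivational intervention, and at 1-month follow-up", and Table 2 lists the motivation and Teachable Moment measures at all three times. F.5.3 treats the follow-ups as two contacts: "All participants will be contacted again one week and one month after receiving the intervention materials".

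The power statement in F.8 starts with "Assuming follow-up of 80% of enrolled participants across the 5 cancer sites" and arrives at a detectable f of .20 with 80% power. F.8 also sets a retention criterion of at least 80% of those with a baseline. Its wording can be read as 80% completing both follow-ups or 80% at each.

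D.2.2 labels the change in "their motivation to quit smoking (preliminary efficacy"), and F.8 adds that "The pilot study will not include a control group".

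The text available contains no analysis set for change, rule for incomplete cases, imputation, mixed model or sensitivity analysis. D.2.4 refers the reader to the statistical section for detail, and the rule is not there. F.5.3 (retention measures) and F.9 (reporting of dropout rates) deal with limiting and disclosing loss, not with how it enters the analysis.

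**The concern.** A conventional repeated-measures ANOVA needs a full row per patient. Someone seen at baseline and one week but not at one month then contributes nothing, not even an observed one-week change. This has two consequences. Precision falls when losses at the two follow-ups are not in the same patients. And if staying in the study is related to scores already recorded, the completers' mean change differs from that of everyone enrolled, in a direction that depends on who leaves.

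The result at stake is the motivation change that the investigators will carry forward as preliminary efficacy. In a single-arm study there is no comparison group in which a similar dropout effect might cancel. Leaving the rule unstated also leaves the choice until after the data are seen.

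**Working it through.** **Inputs.** From F.8: N = 50, follow-up 80%, two-tailed alpha .05, power .80, f = .20. From D.2.3: m = 3 assessments. Not in the documents, hence assumed: equal within-patient correlation ρ (.5, range .3 to .7), sphericity, unit variances, the pattern of loss and its mechanism.

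**1. The plan's own figure.** For a within-patient time effect, λ = n·m·f²/(1−ρ) with df m−1 and (n−1)(m−1). With n = 40 and ρ = .5, λ = 40 × 3 × .04/.5 = 9.6 on (2, 78) df. Power is .78, and 80% power needs f = .204. The stated .20 therefore reproduces. The match is not unique: n = 50 with ρ = .4 also gives about .20.

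**2. Complete cases.**
- Same 20% miss both follow-ups: 50 × .8 = 40. Power .78.
- 80% at each visit, independent losses: 50 × .8 × .8 = 32. λ = 7.68, power .68.
- 80% at each visit, different patients lost: 50 − 10 − 10 = 30. λ = 7.20, power .64.

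On all available data, power is about .80 to .81 in all three (approximate, linear trend).

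**3. Precision of one-month change (SD units).** The complete-case SE is √(2(1−ρ)/n). The all-data SE comes from inverting the summed information of each pattern under covariance ρ. When both follow-ups are lost together it has the closed form √((1−ρ²)/40 + (1−ρ)²/50); at ρ = .5 this is √(.01875 + .005) = .154.

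| Pattern | Complete n | SE complete, ρ = .5 | SE all data, ρ = .5 | Reduction, ρ = .3 / .5 / .7 |
|---|---|---|---|---|
| Both follow-ups lost together | 40 | .158 | .154 | 3.6 / 2.5 / 1.5% |
| Only one month lost | 40 | .158 | .153 | 3.9 / 3.4 / 3.0% |
| Independent losses | 32 | .177 | .153 | 14.0 / 13.4 / 13.0% |
| Losses in different patients | 30 | .183 | .153 | 16.8 / 16.3 / 15.9% |

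If only one month is lost, the SE of one-week change falls from √(1/40) = .158 to √(1/50) = .141.

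**4. Bias.** Simulation of 1,000,000 patients per scenario: trivariate normal, no true change, ρ = .5, 20% lost at one month, logistic loss with slope 0.7 to 1.2 per SD, low scorers lost. Signs reverse if high scorers are lost.

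| Loss depends on | Complete cases, one week | Complete cases, one month | Likelihood, one month |
|---|---|---|---|
| Baseline (observed) | −.06 to −.10 | −.06 to −.10 | about 0 |
| One-week level (observed) | +.07 to +.10 | 0 | about 0 |
| One-week change (observed) | +.13 to +.20 | +.07 to +.10 | about 0 |
| One-month level (unseen) | 0 | +.07 to +.10 | +.09 to +.14 |
| Average of the three scores (partly unseen) | 0 | 0 | +.04 to +.06 |
| One-month change (partly unseen) | +.07 to +.10 | +.13 to +.20 | +.09 to +.14 |

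In the first three rows the likelihood bias is at most .004 SD. If 20% are lost separately at each visit by baseline score (about two thirds complete), complete-case bias is larger, about −.12 to −.17 SD. In two of the three unseen-score rows the likelihood estimate is the more biased.

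**The case against.** The strongest reply is that very little depends on this. Aim 2 is about feasibility and acceptability ("We will evaluate if the intervention is feasible (e.g., screening, recruitment, completion of assessment measures, and follow-up")). Those are analysed descriptively, and D.2.7 bases the step to a larger trial on demand, feasibility and acceptability. In an uncontrolled pilot, change cannot be attributed to the booklet under either analysis. This stands, and it keeps the importance modest.

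Second, the larger precision gain needs 80% at each visit with losses that do not coincide. The retention wording more naturally means both visits, and n = 40 fits the stated f at correlation .5. On that reading the gain is only a few percent. This also stands, but the plan does not settle which reading is meant.

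Third, the bias rests on assumed mechanisms. At correlation .5 with 20% lost at one month, it is below one standard error (about .16 SD) at that visit. True, though the documents give no reason to rule those mechanisms out.

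Four stronger readings are not supported:
- A reader might infer that the plan discards incomplete cases. It does not say so; it is silent, and dropping them is only the usual behaviour of the named method.
- The separate payment "for completing the 1-month follow-up in cash if the study is conducted in person" might suggest that one-month loss is expected. F.5.3 offers it to improve retention, so it is not evidence of that.
- The power figure might seem wrong. It reproduces; what is missing is the correlation and sphericity behind it.
- A dropout effect might seem undetectable without a control group. Comparing completers with dropouts on recorded scores can reveal loss related to those scores.

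**Conclusion.** The point holds, with modest weight. F.8 names a method that, as normally run, needs all three assessments, assumes 20% loss, and gives no rule for partial data. The mixed model's precision gain is small if the same patients miss both follow-ups or only one month is missed, and moderate if losses at the two visits are independent or in different patients. Its protection against bias covers only loss that depends on recorded scores. It should not be presented as a general remedy for dropout: where loss follows unseen motivation it can do worse than complete cases. Nor does it supply the missing control group. Feasibility, acceptability and the progression criteria are untouched. The sizes rest on assumed correlations of .3 to .7 for precision, on correlation .5 and slopes of 0.7 to 1.2 per SD for bias, and on assumed loss patterns; none of these is given in the documents.

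**What to change.** For the continuous scores, replace the ANOVA sentence in F.8 with:

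> Change will be estimated with a linear mixed model for repeated measures (time categorical, unstructured covariance, small-sample degrees of freedom) using all available assessments from everyone with a baseline; completers and dropouts will be compared on baseline and, where available, one-week scores.

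For the Contemplation Ladder only, which D.2.3 names as the main motivation measure, add one sensitivity analysis. Multiply impute missing one-month scores, shift them both up and down by a few stated amounts (for example 0.5 and 1 baseline SD), and report whether the sign and confidence interval of the one-month change alter. With 20% missing, a 1 SD shift moves the mean change by 1 × .20 = .20 SD. Both directions are needed because the documents do not say who is likely to leave.

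As a clarification, state the correlation and sphericity assumed for f = .20, and whether 80% means both follow-ups or each.

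Cost: SAP wording and a little more analysis work, and a main model that relies on loss depending on observed scores. No new data, visits or patients.
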